- 8.4.10 **Side effects.** Hematologic: Myelosuppression; nadir of WBC and platelet depression occurs approximately 21-25 days after treatment. Dermatologic: Alopecia; facial flushing; extravasation may result in severe pain but has not resulted in tissue damage. Rapid IV push may result in pain along injection site or thrombophlebitis. Gastrointestinal: Severe nausea and vomiting which characteristically lessens with each subsequent daily dose. Hepatic: Increased AST, ALT. Renal: Increased serum creatinine, BUN. Neurologic: Facial paresthesia. Other: Flu-like syndrome (with fever, malaise, myalgia) rarely occurs about 7 days after treatment and lasts 1-3 weeks. Rarely Anaphylaxis.
- 8.4.11 **Nursing/patient implications.** Administer prophylactic and prn antiemetics. Monitor CBC, platelet count. May cause pain, burning of the vein with rapid administration. This can be minimized by decreasing the rate of infusion.

9 9.0 STATISTICAL CONSIDERATIONS

9.1 This is a phase II study.

9.2 Analysis of the Conduct of the Study.

- 9.2.1 Data from patients who do not receive the three cycles of AVD chemotherapy or follow-up through 30 days after the last study drug dose due to termination, death, or noncompliance will be tabulated and described. Protocol violations during treatment and follow-up will be listed. Additional analyses will include summaries of patient demographics, baseline characteristics, compliance, and concurrent treatments.
- 9.2.2 The definition of an evaluable patient will be as follows: patients who complete/receive a minimum of at least the 2 initial SGN-35 lead-in doses of therapy and at least 3 cycles of AVD chemotherapy will be considered evaluable for efficacy (response).

9.3 Phase II Efficacy Analysis.

- 9.3.1 The sample size for this study was calculated using a Simon's two-stage design. If the study completes both stages, with an approximate 5-10% loss to follow-up rate, approximately 48 patients will be enrolled, for a total of 45 evaluable patients.
- 9.3.2 The primary endpoint of the phase II portion of this study is the complete remission (CR) rate among older patients with Hodgkin Lymphoma receiving sequential SGN-35 therapy with adriamycin, vinblastine, and dacarbazine chemotherapy (S-AVD). This CR rate for the primary endpoint will be assessed at the completion of AVD chemotherapy (i.e., prior to SGN35 consolidation). Patients who are deemed 'chemotherapy intolerant' (i.e., do not complete 6 cycles of AVD chemotherapy) and have achieved a PR or CR may continue to SGN35 consolidation. Of note, all patients will be 'counted' towards the primary objective of CR rate at the end of AVD chemotherapy on an intent-to-treat basis. Patients who are designated chemotherapy intolerant (i.e., stop AVD chemotherapy prematurely), will have their remission rate analyzed for the primary objective at the time of stopping chemotherapy. These patients will still be followed for other/secondary study endpoints.
- 9.3.3 A true CR rate of 70% would be considered promising in this population, whereas a true complete response (CR) rate of 50% would not be

considered worthy of further study. A two-stage Simon optimal design will be used with 22 patients (21 evaluable patients who are eligible and begin protocol therapy) in the first stage and 26 patients (24 evaluable patients who are eligible and begin protocol therapy) in the second stage. Maximal type I error = 0.05, type 2 error = 0.2.

- 9.3.3.1 If 12 or more CRs are observed in the first stage among the 21 evaluable patients, accrual will continue to the second stage (n=24 evaluable patients in the 2nd stage of the Simon 2-stage).
- 9.3.3.2 If the 21st evaluable patient has enrolled to this study and fewer than 12 CRs have been observed/confirmed, then subsequent accrual to the study will be suspended for lack of adequate response. Once 12 CRs have been confirmed, then the trial may proceed (re-open to accrual if suspended) to the 2nd stage of the Simon 2-stage trial.
- 9.3.3.3 This treatment will be considered promising for further study if 27 or more of the 45 evaluable patients demonstrate CR.
- 9.3.3.4 The probability of stopping at the first stage is 0.07 if the true CR rate is 70% and is 0.67 if the true CR rate is 50%. With 45 evaluable patients, the probability of concluding this treatment is promising for further study is 0.9 and 0.1 assuming a true underlying CR rate of 70% and 50%, respectively. The maximum 90% two-stage confidence interval width for response is 0.26.
- 9.3.4 The incidence of overall response rate (CR and PR) and CR rate to induction SGN35 x 2 cycles will be reported for the initial 22 patients where PET is being employed. In exploratory analysis, outcome measures of PFS and OS will be analyzed for early responder vs non-responders at this timepoint. Patients will be dichotomized for CR/PR vs <PR and PET - vs. PET +.
- 9.3.5 We will also investigate time to progression free survival (PFS), defined as the time from registration to the earlier of disease progression or death from any cause without documentation of disease progression. The exponential Wald test will be used for the PFS analysis. With 45 evaluable patients, an accrual duration of 15 months and an additional follow-up duration of 3 years, there will be approximately 90% power to detect an

improvement in 2-year PFS rate from 45% (corresponding to median PFS 1.7 years) to 65% (corresponding to median PFS 3.2 years), using a one-sided type I error rate of 0.08. We assumed an exponential distribution for PFS and a uniform distribution for patient's entry to the study. The expected PFS event number would be about 20 at the time of analysis.

- 9.3.6 Estimates of the response rate based on CR rate, overall response rate (CR and PR) and the tumor control rate (CR, PR, and stable disease (SD)) will be provided together with the exact two-sided 95% confidence intervals. FDG-PET scanning will be incorporated as a component to assess response rate according to current/updated lymphoma restaging guidelines. The probability of a response in each category will be estimated using the proportion of subjects falling into the response category, that is, (number of subjects with response in that category)/(number of subjects evaluated). For progression-free survival and duration of response the Kaplan-Meier procedure will be used to characterize the survivorship function. Median time-to-events and the corresponding two-sided 95% confidence intervals will be provided for each of these variables. In all estimation we will consider using estimators and confidence intervals appropriate for sequential trials along the lines outlined in Cheng and Shen (Biometrics 60, 910-918) and G Yin and Y Shen (Biometrics 61, 2005).

9.4 Safety Analysis.

- 9.4.1 All patients who receive SGN-35 treatment will be included in the safety summaries and analyses. The safety and tolerability of therapy will be examined by: Extent of exposure to SGN-35 (dose, duration, and number of patients), Detailed summary of deaths by time to death (using Kaplan-Meier methods) and by cause of death, Detailed examination of AEs, Laboratory test results, Vital signs or other physical findings.

9.5 Adverse Events.

- 9.5.1 Adverse events will be classified by body system and preferred term using NCI CTCAE v4. Frequency tables at the patient level will summarize events. Frequency tables by category of event (serious, related), and by NCI CTCAE grade will be presented by dose regimen.

9.6 Laboratory Parameters.

- 9.6.1 Descriptive statistics (mean, standard deviation, mean change from baseline) of laboratory values will be presented. Individual patient graphs

will be displayed and reviewed for clinically relevant changes. Laboratory values of WBC, hemoglobin, absolute neutrophils, platelets, ALT, AST, bilirubin, and creatinine will also be summarized by NCI CTCAE grade.

9.7 Overall survival

9.7.1 Overall survival is defined as the date of study entry to the date of death.

9.7.2 Patients will followed for a total of 3 years for survival and then per local institutional guidelines.

9.8 Progression-Free Survival

9.8.1 Progression-free Survival (PFS) is defined as the time from entry onto study until lymphoma progression or death from any cause. PFS reflects tumor growth and, therefore, occurs prior to the endpoint of overall survival. In addition, PFS is not confounded by the administration of subsequent therapy. Whether a prolongation of PFS represents direct clinical benefit or a surrogate for clinical benefit depends on the magnitude of the effect and the risk-benefit ratio of the therapy under investigation. Unlike survival, the precise date of progression is generally unknown. It may be defined as the first date of documentation of a new lesion or enlargement of a previous lesion, or the date of the scheduled clinic visit immediately after radiologic assessment has been completed. Where there is missing information, censoring of the data may be defined as the last date at which progression status was adequately assessed or the first date of unscheduled new anti-lymphoma treatment.

9.9 Time to treatment failure.

9.9.1 Time to treatment failure (event-free survival) is measured from the time from study entry to any treatment failure including discontinuation of treatment for any reason, such as disease progression, toxicity, patient preference, initiation of new treatment without documented progression, or death.

9.4 Freedom from progression.

9.9.2 Freedom from progression is measured form the time of study entry to the progression of disease. Other causes of treatment failure as noted above in

time to treatment failure are not included in freedom from progression. This end point pertains to the control of disease.

9.10 Quality of life (QoL) assessments.

9.10.1 Although the study is designed as two-stage optimal design study for effectiveness outcome = percent CR rate, QoL analysis will also be powered to show reasonable QoL effect. From literature we gather that functional well being measures have an SD = 6, while FACT-G has SD=16. Looking at After-Before measures, with correlation = 0.5 and equal SD's, for a null hypothesis of no difference between After and Before, and a two sided alternative hypothesis, at $\alpha=5\%$, with $n=21$ patients in the first stage, we have 69% power to reject the null hypothesis in favor of alternative = 9 points for FACT-G. Similarly, if the study goes into second stage, $n=42$ patients gives 82% power to reject H_0 in favor of H_1 if the observed difference is 7 points for FACT-G. Similar results hold for functional well being measures.

9.11 Co-Morbidity assessment.

9.11.1 We will collect the number of co-morbidities for each patient at baseline and at the end of completion of all therapy utilizing the Cumulative Illness Rating Scale and assess the relationship between CIRS score and outcome (CR, DFS, PFS).

The comprehensive geriatric assessment (CGA) has been developed as a procedure to assess the objective health status of elderly persons.⁵²⁻⁵⁵ The CGA is considered to be more effective than standard medical evaluation for the care of the elderly. Initially, use of a CGA was based on its ability to predict morbidity and mortality in the general geriatric population, although accumulating data show the benefits of using the CGA specifically in patients with cancer.^{53,54,56} Comorbidity is an essential part of the CGA. Several comorbidity scales have been used in research, although the Cumulative Illness Rating Scale (CIRS) is one of the more prominent tools utilized in geriatrics.^{53,57} The CIRS measures chronic medical illness burden while taking into account the severity of chronic diseases. The CIRS has been revised to reflect common problems of elderly people and was renamed the Cumulative Illness Rating Scale for Geriatrics (CIRS-G);⁵⁸ this version has subsequently been validated.⁵⁹ Furthermore, several recent cancer related studies have validated the relevance of the CIRS to define comorbidities among oncology patient populations, some of which correlated with survival.^{60,61}

For binary outcomes such as CR, logistic regression will be used to assess the relationship with CIRS score; for time-to-event outcomes, the method of Kaplan and Meier and the log rank test, as well as Cox proportional hazards models, will be used to assess the association with co-morbidity.

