5.3.4.2 Growth factor

Granulocyte colony stimulating factor (e.g., G-CSF) may be used at the discretion of the treating physician as above and in accordance with ASCO guidelines; however as noted in Section 5.3.3.1, G-CSF would be advocated (filgrastim) vs pegfilgrastim. Please record all granulocyte (or erythrocyte) colony stimulating factors on the treatment forms.

5.3.5 Re-staging.

All patients will have re-staging FDG-PET and re-staging CTs of the neck/chest/abdomen/pelvis performed after the 3rd cycle of AVD.

Recommended timing of these scans are between days 22 and 25 of the 3rd cycle. All patients will also have re-staging CTs of the neck/chest/abdomen/pelvis performed at the completion of AVD (i.e., after the 6th cycle).

FDG-PET will only be repeated at this time (end of AVD) if the patient has not entered into complete remission (CR). See **Section 6.0** for further details regarding assignment of response and see Table 3 Schedule of Activities in Section 7.0 for additional details. Any patient who has not achieved a CR or PR after the 6 cycles of AVD should be taken off study at this point and not proceed with SGN-35 consolidation therapy.

5.4 SGN-35 consolidation.

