7 STUDY PARAMETERS

7.1 Schedule of Study Activities. See *Table 4 below* for the Study Activities.

- 7.1.1 **Pre-cycle testing.** Laboratory assessments must be done within 30 days before beginning study treatment (testing may be completed on day 1 of each cycle, but must be done prior to treatment). Measurements of measurable disease (as in Section 6.1.1) or non-measurable disease (as in Section 6.1.2) must be completed within 60 days prior to starting treatment. Staging bone marrow and cardiac testing (e.g., echocardiogram) may have been done within the prior 90 days before starting treatment. A window of +/- 2 days is permitted for all scheduled visits, tests, and procedures.
- 7.1.2 **Treatment Schedule.** Patients will be seen by a physician every 3 weeks during the SGN-35 “lead in” phase, every 4 weeks during AVD therapy, and every 3 weeks during SGN-35 consolidation. A window of +/- 2 days is permitted for all scheduled visits, tests, and procedures.
- 7.1.3 **Follow-Up Visit Schedule.** Patients with CR, PR, or SD will return for a follow-up examination 30 days after their last treatment dose. Early termination patients and patients with PD will return for a final study visit (including imaging) 30 days after their last respective treatment dose.
- 7.1.4 **Concomitant Medications.** All concomitant medications will be recorded from screening through study discontinuation.
- 7.1.5 **Eastern Cooperative Oncology Group (ECOG) Performance Status Assessment.** The patient’s ECOG performance status will be assessed during screening (within 14 days before beginning study treatment). To be eligible for enrollment, patients must have a score of 0, 1, or 2, according to the ECOG scale (see Appendix I).
- 7.1.6 **CT scan and PET scan.** Patients will undergo CT scans of the chest, abdomen and pelvis +/- neck and FDG-PET scanning prior to cycle 1. Scans must be done within 60 days prior to day 1, cycle 1. The baseline CT scan may be done concurrently with the PET scan, however oral contrast needs to be used (use of intravenous contrast for the diagnostic CT is encouraged, but not mandatory).

Table 4. Schedule of Activities.

Parameter	Pre-study	SGN-35 lead-in Cycles¹	AVD¹⁵ Cycles²	SGN-35 consolidation¹⁵ Cycles³	Post-Therapy Follow-up
Assignment of IPS score	X				
History and Physical examination	X	X	X	X	X ¹³
Performance Status	X	X	X	X	X ¹³
Tumor Measurements by Physical Exam (if applicable)	X	X	X	X	X ¹³
CBC and Differential ⁴	X	X	X	X	X ¹³

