9. Combined PET/CT scan will be sufficient if the PET/CT is performed with oral contrast (intravenous contrast is encouraged, but not mandatory); if PET/CT is without oral contrast, then separate/dedicated CTs of chest/abdomen/pelvis (in addition to PET/CT) must be obtained. Please see Section 6.6 for further guidelines on recommended interpretation of PET scans.				
10. The first 22 evaluable patients entered on the study will have a repeat FDG-PET after the 2 "lead in" cycles of SGN35. This should be completed the week prior to planned initiation of AVD chemotherapy. All patients entered on study will have FDG-PET and CTs performed prior to day 1 of cycle 4 of AVD therapy (after day 15 of cycle 3). Thereafter, once a patient enters complete remission (CR), then only CT's (chest/abdomen/pelvis) should be obtained (not both PET/CT and dedicated CTs). All patients will have re-staging scans performed at the end of AVD chemotherapy (i.e., prior to start of SGN35 consolidation therapy).				
11. See Appendix III and Appendix IV for further details/methods for completion. This includes Co-morbidity assessment (Appendix III) and Activity of Daily Living (ADL) assessment (Appendix VI). Obtain once at baseline (pre-treatment) and then repeat once at the completion of all therapy.				
12. See Section 6.9 for exact timing and description and Appendix IV for Quality of Life forms.				
13. 30 days (+/- 2 days) after the last dose of treatment, patients should have repeat re-staging CTs +/- FDG-PET completed. Thereafter, the follow-up schedule will be office visits with blood tests q 3 months and re-staging CTs q 6 months for 3 years, then per local institutional guidelines. Patients who stop treatment early due to AEs or PD will also follow this schedule.				
14. See Table 4 in Section 12.3.3 for full explanation of which blood tubes (i.e., ACD/yellow, EDTA/purple, and red top) and timing (e.g., baseline/pre-SGN35, after 2 cycles of SGN35 lead-in, and after completion of AVD chemotherapy) of correlative blood studies.				

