10.5 Termination of Treatment and/or Study Participation

Patients will be informed that they have the right to withdraw from the study at any time for any reason, without prejudice to their medical care. The investigator also has the right to withdraw patients study treatment for any of the following reasons:

- Intercurrent illness
- Occurrence of an unacceptable adverse event
- Patient request (follow-up may still be permitted unless patient withdraws consent from the study as a whole)
- Protocol violations
- Non-compliance
- Administrative reasons
- Failure to return for follow-up
- General or specific changes in the patient's condition unacceptable for further treatment in the judgment of the investigator
- Progressive disease at any time

If treatment is ongoing at the time of termination, patients should return 30 days after the last study treatment for a “termination visit” that includes the assessments specified for the 30-day follow-up visit. If this is not possible or if the patient has completed study treatment more than 30 days before, these assessments should be done at the time of termination.

If a patient has terminated the study as a whole (withdraws consent), no further data collection and submission is permitted, except for follow-up of AE’s present at the time of termination. If, however, a patient is withdrawn from treatment (but not the study as a whole), follow-up for survival endpoints will continue.

Patients may choose to stop study treatment and/or withdrawn from the study as a whole for any reason without jeopardizing their relationship with their health care providers.

- 10.5.1 **Accountability for Study Drug.** Seattle Genetics Clinical Affairs (the Supporter) or its designee will ship vials of SGN-35 directly to each study center.

The individual receiving the shipment must verify the quantities received. The Clinical Supplies Shipping Receipt contained in the shipment must be signed, dated, and returned to the Supporter or its designee. An overall summary of all clinical supplies received, used, and returned per patient must be maintained by each study center. Seattle Genetics will provide full accountability for shipments of drug to individual sites. Seattle Genetics will NOT assume accountability of drug within the individual sites.

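### Follow-up of stable-disease non-responders after AVD is stated inconsistently, and PFS censoring at new lymphoma treatment is left open, so 2-year PFS can be overestimated

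*Combined protocol and SAP*

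**What the plan says.** **Leaving the study.** Section 5.3.5 states: "Any patient who has not achieved a CR or PR after the 6 cycles of AVD should be taken off study at this point". The note to the schema in 5.1 and Table 4 footnote 15 say the same. For early terminations and progressive disease (PD), 7.1.3 says that "patients with PD will return for a final study visit (including imaging) 30 days after their last respective treatment dose".

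**Staying in follow-up.** Table 4 footnote 13 sets a scan 30 days after the last dose, then visits every 3 months and CT every 6 months for 3 years, and adds: "Patients who stop treatment early due to AEs or PD will also follow this schedule". Section 7.1.3 lists SD with CR and PR for the 30-day examination. Section 9.7.2 follows patients for survival for 3 years. Section 10.5 says that for a patient withdrawn from treatment but not from the whole study, "follow-up for survival endpoints will continue". Appendix VIII asks for the response form every 6 months, and the follow-up form, for 3 years after treatment ends.

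**Censoring.** Section 9.8.1 defines PFS as time to progression or death from any cause. Where information is missing, it allows censoring at the last date progression status was "adequately assessed or the first date of unscheduled new anti-lymphoma treatment". The wording is permissive, and neither date has priority. The same paragraph says that later therapy does not confound PFS. Section 9.9.1, by contrast, counts new treatment without progression as a failure for time to treatment failure (TTF).

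**The concern.** A patient with SD after six AVD cycles has no PFS event yet, receives no consolidation, and may well be given other lymphoma treatment. Read literally, *off study* ends that patient's assessments. This creates the missing information that 9.8.1 requires before it allows censoring at the new treatment. Kaplan-Meier estimation would then give this patient the later prognosis of those who responded.

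The documents give some reason to expect a worse prognosis. In the retrospective series in 1.3, less than CR to initial therapy predicted poorer OS (hazard ratio 9.32), although that group includes PR.

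The trial has one arm, and 9.3.5 tests 2-year PFS against a fixed 45%. An upward shift in the estimate is therefore not offset by a similar shift in a comparator. Because the censoring rule is optional, it could also be chosen after the data are seen.

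**Working it through.** **1. The plan's own PFS figures (9.3.5).** Inputs: 45 patients, "an accrual duration of 15 months and an additional follow-up duration of 3 years", uniform entry, exponential PFS, 45% against 65% at 2 years, one-sided 0.08.
- Hazard λ = −ln S(2)/2 = 0.399 and 0.215 per year. Medians ln 2/λ = 1.74 and 3.22 years, which agree with the stated 1.7 and 3.2.
- Expected events = 45 × {1 − [exp(−λF) − exp(−λ(F+A))]/(λA)}. With A = 1.25 and F = 3 this gives 34.3 (null) and 24.3 (alternative). The plan says about 20.
- Power is at least 94.9% in every version of the Wald test tried, against a stated 90%. With F = 2 the event count is 19.4, and the log-hazard version with variance under the alternative gives 90.5%. The stated figures thus fit 2 years of added follow-up rather than 3. That is a separate matter. What counts here is that the calculation has no term for censoring at new therapy.

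**2. When the off-study rule applies.** 2 × 21 + 6 × 28 = 210 days, so t₀ = 0.575 years (week 30).

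**3. Kaplan-Meier bias, by share of all patients.** Assumptions, none from the documents:
- A share f is event-free with SD at t₀, and all of them are censored there.
- Their true PFS at 2 years is p.
- The other patients are exponential with 2-year PFS r.

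True S(2) = f·p + (1−f)·r, so r = (S(2) − f·p)/(1−f). With r₀ = r^(t₀/2), Kaplan-Meier gives [f + (1−f)·r₀]·r/r₀ = f·r/r₀ + (1−f)·r.

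Example: S(2) = 0.45, f = 0.10, p = 0.10. Then r = 0.44/0.90 = 0.489, r₀ = 0.814, and the estimate is 0.060 + 0.440 = 0.500.

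| f | p = 10% | p = 25% |
|---|---|---|
| 5% | 47.4% | 46.6% |
| 10% | 50.0% | 48.4% |
| 15% | 52.8% | 50.2% |

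All entries are for a true 45%. At a true 65% with f = 10% and p = 10%, the estimate is 71.8%.

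**4. Sensitivity to prognosis.** Now let s be the SD share among patients event-free at t₀, and c their chance of staying progression-free from t₀ to 2 years. With S₀ the overall PFS at t₀ (0.795 for a true 45%), the estimate is (S(2) − S₀·s·c)/(1−s). For s = 2–15%:
- c = 0 (upper bound): 45.9–52.9% for a true 45%, and 66.3–76.5% for a true 65%.
- c = 25%: bias +0.5 to +4.4 points (true 45%), or +0.9 to +7.6 (true 65%).
- c = 50%: +0.1 to +0.9 (true 45%), or +0.4 to +3.7 (true 65%).
- c = 90%: 44.5% falling to 40.3% for a true 45%, so the sign reverses.

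The bias is zero at c = S(2)/S₀ = 0.45/0.795 = 57%.

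**5. Effect on the test.** In simulated 45-patient trials at the null (6,000 per setting, c = 25%), rejection at nominal 0.08 was 0.108 (s = 5%) and 0.151 (s = 10%) with censoring, against 0.076 and 0.080 with full follow-up. The simulation error is about √(0.08 × 0.92/6000) = 0.0035. At s = 15% the rates were 0.216 and 0.102, so part of the excess there comes from the exponential model no longer fitting.

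**The case against.** A reader might infer that the worst responders leave the risk set and that PFS and OS are therefore inflated. The documents do not support that.

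- Patients with PD already count as PFS events. Only SD without documented progression is exposed.
- The first part of footnote 13 covers patients generally. Its closing sentence adds those who stop for AEs or PD and excludes nobody.
- Section 7.1.3 names SD among those returning at 30 days. Section 10.5 links leaving the whole study to withdrawal of consent, which an SD patient stopped by rule has not done.
- Appendix VIII ties the 3-year forms to the end of treatment, with no exception for SD.
- Censoring at new treatment is conditional on missing information, optional, and one of two dates. If follow-up continues, the condition will seldom be met.
- OS has no censoring at new therapy, and 9.7.2 and 10.5 provide survival follow-up.

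All of this stands, and it makes continued follow-up the more natural intention. Two things remain. *Off study* appears in three places and conflicts with that intention, as does *final* in 7.1.3 for PD patients whom footnote 13 follows for three more years. And 9.8.1 leaves the handling of new therapy open.

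**Conclusion.** The concern holds as a contradiction to be reconciled and an open analysis choice, with a conditional upward bias in PFS. It does not establish that PFS will be overestimated.

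If SD non-responders are dropped and censored at a switch of therapy just after AVD, a true 45% reads about 47–53%. This assumes an SD share of 5–15% and 2-year PFS of 10–25% in those patients. That is roughly 2 to 8 of the 20 points the test looks for. At a true 45% the bias is under 1 point if half stay progression-free, and it turns negative above about 57%.

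The SD share is not given. The response rates of 88% (1.3) and 70% (1.5) leave 12–30% without a response, of which SD is an unstated part.

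The CR primary endpoint is unaffected. TTF already counts these failures, and OS inflation is not shown.

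**What to change.** 1. Reconcile 5.1, 5.3.5 and Table 4 footnote 15 with 10.5 by writing off protocol treatment in place of *off study*. The rule on consolidation itself is not at issue.
2. State that the progression and survival follow-up in footnote 13 applies to every patient who stops treatment for any reason, short of withdrawn consent, and remove *final* from 7.1.3.
3. In 9.8.1, fix one PFS rule before the data are seen: follow to documented progression or death regardless of new therapy, and censor only at the last adequate assessment. Add a sensitivity analysis that counts unscheduled new lymphoma treatment as an event. Which rule is primary is partly convention. The gain lies in choosing it in advance and reporting the alternative.
4. Amend the sentence saying that later therapy does not confound PFS so that it agrees with the chosen rule.

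The cost is wording, plus visits and scans already scheduled for other patients. The PFS estimate may come out slightly less favourable.
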